5.0 RECRUITMENT, CONSENT AND ENROLLMENT

5.1 Recruitment

Participants will be recruited from several channels including outreach to sleep clinics, sleep physicians and providers, Sip2Sleep[®] customer base via the product website, People Science community base and social media. Social media channels may include Facebook, Reddit, Instagram, and Google.

Recruitment outreach will consist of IRB approved advertising by email, digital flyers/postcards, printed flyers and word of mouth to patients.

A study landing page will provide information about the study and criteria for qualification. The landing page will lead to an IRB approved pre-screening questionnaire to determine qualification and then collect first and last name, email, phone number, and zip code of qualified individuals. New leads will receive further instructions by email to continue the enrollment process.

5.2 Consent

Virtual electronic informed consent, including a study specific privacy authorization and the California subject’s bill of rights (as applicable) will be conducted through a HIPAA compliant cloud-based platform to obtain electronic consent that will ensure that the consenting process follows all required elements (see Section 7.0). A digital copy of the signed consent will be stored with the participant’s profile in the study data platform which is the same technology used for electronic consent. In addition, a copy of the signed consent document will be available to the participant within the CHLOE app.

5.3 Enrollment

Eligible participants who provide virtual electronic consent will be automatically registered into the study by CHLOE (see Section 12.6). Participants will be asked to complete a screening ISI assessment and 3 additional screening surveys to review demographics, medical history, and product shipment address if eligible.

After confirmation of eligibility, the participant will be enrolled in the study and receive an email with instructions to start study assessment in CHLOE and await Direct to Consumer (DTC) shipment of the Sip2Sleep[®] study product.

6.0 STUDY PROCEDURES

6.1 Study Overview

[figure not shown]

Figure 1. Study Design

Upon enrollment, the study assessments can be accessed via CHLOE mobile app available on Apple iOS and Android devices as well as any web browser. The participant's activities are as follows:

Screening (Day -7 to Day -1):

- Informed Consent
- Complete demographic and medical history data intake.
- Screening Insomnia Severity Index (ISI) assessment.
- Provide preferred shipment address for product shipment during Baseline.

Baseline Period (Day 1 to Day 7):

- Complete Insomnia Severity Index and Generalized Anxiety Disorder-7 (Day 1 only).
- Begin discontinuation of non-prescription products used for sleep.
- Begin nightly use of personal health tracking wearable device through Day 28.
- Complete daily survey to review objective data (sleep duration and sleep latency) from wearable device collection and answer questions about their prior night's sleep quality and level of alertness since waking.
- Receive shipment of study product and instructions for use.

Product Use Period (Day 8 to Day 14):

- Complete Insomnia Severity Index and Generalized Anxiety Disorder-7 (Day 8 only).
- Continue nightly use of personal health tracking wearable device through Day 28.
- Complete daily surveys to review objective data (sleep duration and sleep latency) from wearable device collection and answer questions about their prior night's sleep quality and level of alertness since waking.
- Administer nightly dose of study product 30-60 minutes prior to lying down in bed through Day 14.

No Product Use Period (Day 15 to Day 21):

- Complete Insomnia Severity Index and Generalized Anxiety Disorder-7 (Day 15 only).
- Continue nightly use of personal health tracking wearable device through Day 28.
- Complete daily surveys to review objective data (sleep duration and sleep latency) from wearable device collection and answer questions about their prior night's sleep quality and level of alertness since waking.

Product Use Period (Day 22 to Day 28):

- Complete Insomnia Severity Index and Generalized Anxiety Disorder-7 (Day 22 only).
- Continue nightly use of personal health tracking wearable device through Day 28.
- Complete daily surveys to review objective data (sleep duration and sleep latency) from wearable device collection and answer questions about their prior night's sleep quality and level of alertness since waking.
- Administer nightly dose of study product 30-60 minutes prior to lying down in bed through Day 28.

End of Study (Day 29):

- Complete Insomnia Severity Index and Generalized Anxiety Disorder-7.
- Complete surveys to review objective data (sleep duration and sleep latency) from wearable device collection and answer questions about their prior night's sleep quality and level of alertness since waking.
- Complete Experience Survey.

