1.0 OBJECTIVES AND ENDPOINTS

Objectives	Endpoints/ Measurements
Primary Objective	

 To observe the effect of the Sip2Sleep® product on sleep quality for participants with self-reported sleep disturbance 	
 Change in average sleep quality score by 1 point as measured by daily 10-point visual analogue rating scale (VAS) from baseline and 1 week of no product use
Secondary Objectives	

 To assess the effect of Sip2Sleep® product on symptoms of sleep disturbance To assess the effect of Sip2Sleep® product on anxiety To assess the effect of Sip2Sleep® product on the level of alertness during the daytime 	
 Change in Insomnia Sleep Index (ISI) by 4.5 points from baseline and 1 week of no product use Change in Generalized Anxiety Disorder-7 (GAD-7) by 4.5 points from baseline and 1 week of no product use Change in average level of alertness during the daytime score by 1 point as measured by daily 10-point visual analogue rating scale (VAS) from baseline and 1 week of no product use
Exploratory Objectives	

 To observe the change in sleep duration via personal health tracking wearable device To observe the change in sleep latency via personal health 	
 Change in average nightly sleep duration as measured via personal health tracking wearable device from baseline and 1 week of no product use Change in average nightly sleep

tracking wearable device
 
3. To identify improvements for future participant-centered study designs using feedback
	
latency as measured via personal health tracking wearable device from baseline and 1 week of no product use
 
3. Assessment of patient satisfaction survey of study experience including design and use of app-based data collection tools

---	--

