2.2 Overview of and Rationale for the Study Design

The rationale for this study is to determine the effect of a consumer-grade, unique formula called Sip2Sleep®, which is a combination of Montmorency tart cherry extract and Venetron®, a patented, purified, powdered extract derived from the Rafuma leaf, *Apocynum venetum*, on sleep disturbance in adults. Because this product is currently available in the OTC market across the United States, a consumer-driven, decentralized observational clinical research study is well-suited for examining the effect of this formulation on sleep.

Sleep disturbance is highly prevalent and impacted by many interdependent variables. We will examine self-reported sleep disturbance in a broad age-range of adults who have chosen to use this product. The study will incorporate participant reported outcome questionnaires, daily surveys, and the participants' personal health tracking wearable device (e.g. Apple Watch, Fitbit, Smartwatch, etc.) to engage the participant in their sleep health and explore objective digital outcome measures of sleep. An important feature of this consumer-driven study design is to help individual consumers observe the effects of this product on their own sleep patterns during the study itself. There is no "doctor-patient" relationship as part of this research since the participant as a consumer is making the informed choice to take the product and take part in the observational process with self-reported measures. Findings from this study will contribute knowledge toward the design of future sleep research studies, the improvement of the Sip2Sleep® product formulation, and may help inform clinical recommendations for adults interested in using alternative products for sleep.

The following self-reporting measures are used in order to evaluate the effect of Sip2Sleep® in adults with self-reported sleep disturbance:

Surveys to reflect sleep quality, sleep latency, total sleep duration and level of alertness during the day to be distributed daily. Sleep quality and level of alertness during the day will be evaluated with a single 10-point visual analogue scale (VAS) and objective sleep data reflecting sleep latency and total sleep duration will be collected from personal wearable devices.

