4.0 STUDY ACTIVITY CALENDAR

Table 4.1 Study Calendar

Protocol Activities	Screening ^a	Study Duration ^b				
		Baseline	Product Use ^c	No Product Use	Product Use ^c	End of Study
Week	Up to 1 Week	Week 1	Week 2	Week 3	Week 4	
Day	Day -7 to -1	Day 1	Day 8	Day 15	Day 22	Day 29
Informed Consent	X					
Demographics	X					
Medical History	X					
Insomnia Severity Index	X	X	X	X	X	X
Eligibility	X					

Daily Objective Data Collection and Surveys ^d		X	X	X	X	X
Use of Study Product			X		X	
Generalized Anxiety Disorder-7		X	X	X	X	X
Experience Survey						X

- a. Screening to occur within 7 days prior to Baseline (Day 1)
- b. Planned duration of study is 4 weeks
- c. Participants to consume Sip2Sleep[®] product 30-60 minutes prior to lying down in bed.
- d. Participants will complete daily surveys to review objective data from wearable device collection and answer questions about their prior night’s sleep quality and level of alertness since waking.

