12.4 Confidentiality/Sharing/Publication

Return or Clinical Use of Research Results

Participants will be shown their study data in real time as they go through the data visualization modules in the CHLOE platform.

Research results will be shared with participants at completion of data analysis. The results of this research may help the participant make decisions in future product purchases and participate in future research studies.

There are no anticipated burdens or financial obligations to research subjects.

Confidentiality

All documents and electronic data will be stored on secure, password-protected computers. Participant confidentiality will be strictly held in trust by the investigators, study personnel, and sponsor. No identifiers will be used in any subsequent publication of these results.

Information/Data Retention, Future Use, and Sharing

Prior to the completion of this research, information will be coded, destroyed, de-identified, or provided to a privacy officer.

Publication

The publication or presentation of any study results shall comply with all applicable privacy laws, including, but not limited to, the Health Insurance Portability and Accountability Act of 1996. Neither the complete nor any part of the results of the study carried out under this protocol, nor

any of the information provided by the sponsor for the purposes of performing the study, will be published or passed on to any third party without the written approval of the Study PI. Any investigator involved with this study is obligated to provide the sponsor with all data derived from the study.

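### The plan does not require the daily sleep quality and alertness ratings to be entered before that night's wearable reading is shown, so the primary VAS can be influenced by the device.

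*Combined protocol and SAP*

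**What the plan says.** Section 6.1 describes the daily survey for the baseline period as "Complete daily survey to review objective data (sleep duration and sleep latency) from wearable device collection and answer questions" on last night's sleep quality and today's alertness. The two product-use periods and the no-product period carry nearly the same sentence. The Day 29 entry reads "Complete surveys to review objective data (sleep duration and sleep latency) from wearable device collection and answer questions" on the same two topics. Footnote d of Section 4.0 covers the whole study: "Participants will complete daily surveys to review objective data from wearable device collection and answer questions".

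The answers feed the main endpoints. Under Section 1.0 the primary endpoint is the change in average sleep quality on a daily 10-point VAS, and a secondary endpoint is the corresponding change for daytime alertness. Section 2.2 makes each a single-item rating. Wearable sleep duration and latency are separate, exploratory endpoints ("To observe the change in sleep duration via personal health tracking wearable device", and likewise for latency).

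Showing participants their data is intended. Section 2.2 calls it an important feature of the design to "help individual consumers observe the effects of this product on their own sleep patterns during the study itself". Section 12.4 (Confidentiality/Sharing/Publication) adds: "Participants will be shown their study data in real time as they go through the data visualization modules" of the app.

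No section requires the rating to come first or withholds the device figures until it has been submitted. Sections 9.3 to 9.6 do not address the display in the analysis.

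**The concern.** A single-item rating of sleep quality is a judgement, and a sleep duration or latency figure seen in the same form is an obvious reference point for it. A participant may then rate partly what the device reported and partly how the night felt. The alertness item in the same survey is open to the same influence.

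What is at stake is interpretation. If the VAS partly follows the device, then agreement between the primary result and the exploratory wearable results is partly built in, and a reader could not treat the two as separate evidence. The VAS change itself could be pulled up or down, depending on what the devices show. The study has no concurrent control group in which such a shift could be observed.

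**Working it through.** **1. The plan's own figure.** Section 9.1 gives SD 2, correlation 0.50, a mean difference of 1, two-sided α = 0.05, a Wilcoxon signed-rank test, n = 47 and at least 90% power.

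- SD of the paired difference = √(2 × 2² × (1 − 0.50)) = 2, so the standardised effect is 1/2 = 0.5.
- A paired t-test (noncentral t) needs n = 44 for 90% power.
- Dividing by the Wilcoxon relative efficiency 3/π gives 44/(3/π) = 46.08, rounded up to 47.
- Power at n = 47 is 90.6% by this method, and 90.8% in a simulation of 20,000 normal samples.

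The sample size reproduces. The point concerns how the endpoint is measured, not this calculation.

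**2. The texts on order, side by side.**

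| Place | Named first | Named second | Order fixed? |
|---|---|---|---|
| 4.0, footnote d | device review | sleep quality and alertness questions | no |
| 6.1, four study periods | device review | the same questions | no |
| 6.1, Day 29 | device review | the same questions | no |
| 2.2, daily surveys | sleep quality | latency and duration, then alertness | no |
| 12.4, Confidentiality | (real-time display of study data) | – | no |

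The operational sections agree with one another, but they repeat one sentence and join the two tasks with *and*. Section 2.2 lists the content differently. The supportable conclusion is that the order is not specified and that the protocol allows the device figures to be seen before the rating.

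**3. Can a size or direction be derived?** The documents give no value for how strongly a rating follows the device. As an assumption only, let the observed change be (1 − w) × T + w × D. Here T is the change the participant would report unaided, D is the change implied by the device in VAS points, and w is the weight given to the device. Take T = 1 and n = 47, and hold the SD of the difference at 2. Each cell shows the observed change and its power by the method of step 1:

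| w | D = 0 | D = 0.5 | D = 1 | D = 1.5 |
|---|---|---|---|---|
| 0.1 | 0.90; 83.8% | 0.95; 87.5% | 1.00; 90.6% | 1.05; 93.0% |
| 0.25 | 0.75; 69.0% | 0.875; 81.8% | 1.00; 90.6% | 1.125; 95.8% |
| 0.5 | 0.50; 37.4% | 0.75; 69.0% | 1.00; 90.6% | 1.25; 98.4% |

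Example: w = 0.5 and D = 0 gives 0.5 × 1 + 0.5 × 0 = 0.50. Over this assumed grid the observed change runs from 0.50 to 1.25 and power from about 37% to 98%. Both directions occur, and nothing in the documents selects a cell.

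**4. The case of no product effect.** If neither the unaided rating nor the device changes, T = D = 0 and the observed change is 0 for every w. If unblinded participants over-rate product nights by an amount b while the device shows no change, the observed change is (1 − w) × b, which is smaller than b. In this model, anchoring to an unchanged device reading creates no spurious difference and dilutes one that comes from expectancy.

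**The case against.** Four arguments have weight.

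*No screen order is stated.* This is correct. The order of words in a sentence is not a specification, and Section 2.2 names sleep quality first. Section 5.3 also uses *review* for surveys that simply collect demographics and medical history, so the daily survey might only capture or confirm the wearable data. A reader might infer that every description puts the device reading before the rating; the documents do not support that. What stands is that no rule prevents that order, and Section 12.4 makes some exposure likely.

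*The review occurs in every period.* This is also correct, and a constant shift in ratings would cancel from the pre/post or on/off difference. A shift that depends on the reading would not necessarily cancel. A reader might infer that the display raises the false-positive rate or strengthens expectancy. The documents give no basis for that, and step 4 of the working shows that the effect could run the other way.

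*Wearables have no corroborating role.* The protocol assigns them none; they are exploratory endpoints. The independence point is therefore a limit on how the results may be read together, not a failure of a planned analysis.

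*Self-observation is deliberate, and participants own the devices.* The display is a legitimate design choice, but it does not require the figures to come before the rating. Because participants can look at their own watch or ring first, no app setting can close the route completely. That limits the benefit of the fix without removing the reason for it.

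**Conclusion.** The point holds as a gap in the protocol. The primary sleep quality VAS and the secondary alertness VAS share a daily survey with a review of the wearable data, the review is named first in Sections 4.0 and 6.1, and no text requires the rating to be entered before the data are seen. The ratings can therefore be influenced by the device and may not be independent of the exploratory wearable endpoints.

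Its size and direction cannot be determined from the documents. The range of 0.50 to 1.25 points in the working rests wholly on assumed weights and assumed device changes, and shows only that either direction is possible. A reader might go further and conclude that the primary endpoint is no longer a self-report; the text does not support this, since it shows an opportunity for influence and not that influence occurs. The planned sample size of 47 is unaffected. The point is worth acting on because the protection is specific and almost free.

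**What to change.** In footnote d of Section 4.0 and in each daily-survey entry of Section 6.1, including Day 29, state that the sleep quality and alertness VAS items are submitted and locked before that night's wearable data are displayed in the app. Add an instruction asking participants not to check their own device's sleep reading before they rate. If the app already works in this order, the protocol needs only to say so.

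The cost is a change of screen order and one line of protocol text. Participants still see all their data on the same day, so the self-observation aim of Section 2.2 is kept. The remaining weakness is that viewing on the participant's own device cannot be fully prevented. The exposure is reduced but not removed, and any reading of the VAS and wearable results together should say so.

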2.0 INTRODUCTION: BACKGROUND INFORMATION & SCIENTIFIC RATIONALE

2.1 Introduction/Rationale for Development

Insomnia occurs in up to 50% of adults in the U.S., while chronic insomnia disorder is estimated to impair 10-15%.¹ Lack of quality and quantity of sleep negatively affects every part of an individual's life, both personally and professionally. Poor sleep is associated with various comorbidities including depression, stroke, cardiovascular disease, obesity, dementia and Alzheimer's disease, and increased risk of developing type 2 diabetes.^{2,3,4,5} Furthermore, there has been an increase in evidence of the long-term harm (i.e., increased risk of cognitive dysfunction and impairment such as Alzheimer's disease) of taking prescription sleep aids such as Ambien, Lunesta, benzodiazepines, and OTC sleep aids like Benadryl.⁶

Sip2Sleep[®] was developed in conjunction with a leading sleep physician who has focused efforts in assisting patients improve sleep problems and insomnia by identifying the root cause(s) of the issues. Sip2Sleep[®] uses a proprietary formula of Montmorency tart cherry extract and Venetron[®].

Montmorency tart cherry is a special kind of cherry that is known to provide a natural source of melatonin. The ruby red pigments in this specific cherry are proanthocyanidins, natural compounds that help increase the brain availability of tryptophan—an essential amino acid and precursor to the natural sleep aid serotonin. Proanthocyanidins inhibit an enzyme (indoleamine 2,3 dioxygenase) that degrades tryptophan, a known predictor of insomnia. The minimization of tryptophan degradation may allow tryptophan to work more effectively in the body while increasing bioavailability for serotonin synthesis, leading to a positive effect on sleep while improving mood and decreasing inflammation.^{7,8}

Researchers at Louisiana State University presented data in 2018 showing that drinking Montmorency tart cherry juice just twice a day for two weeks helped increase total sleep time by nearly 90 minutes among older adults with insomnia. Greater than 75% of participants reported a positive response to the cherry juice with a significantly reduced amount of time to initiate sleep and improved ability to maintain sleep.⁷

Venetron[®] is a patented, purified, powdered extract derived from the Rafuma leaf, *Apocynum venetum*, which is a safe botanical alternative to St. John's Wort. It helps insomnia by:^{9,10,11}

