3.2 Eligibility

Participants must meet all the following criteria on screening examination to be eligible to participate in the study:

Inclusion

1. Age \geq 18 years old
2. Has self-reported sleep disturbance
3. Insomnia Severity Index (ISI) score of \geq 15 at screening
4. Interested in understanding more about the quality of their sleep and chose to use the Sip2Sleep product for sleep
5. Willingness to do a minimum of 1 week wash out of current OTC or other products for sleep (e.g. melatonin, anticholinergics)
6. Willingness to do a minimum of 1 week wash out of any cannabis products
7. Able to receive shipment of the product at an address within the United States
8. If taking prescription hypnotics (e.g. zolpidem, zaleplon, benzodiazepines) or other class of medication for sleep, must be on a stable dose for at least 4 weeks.
9. Able to read and understand English
10. Able to use a personal smartphone
11. Has and is able to use a personal health tracking wearable device (e.g., Apple Watch, Fitbit Smartwatch, Oura Ring, etc.)
12. Able to understand and provide informed consent
13. Able to complete study assessments over 5 weeks

Exclusion

1. Research participants who have no computer, smartphone, and internet access and/or do not use a computer or smartphone
2. Concomitant Therapies:
 - a. Participants taking daily prescription medication for sleep (for example, prescription hypnotics like zolpidem, zaleplon, benzodiazepines) not on a stable dose for at least 4 weeks
 - b. Participants receiving Cognitive Behavioral Therapy for Insomnia (CBTi)

- c. Participants receiving any investigational therapies or treatments
3. Other Illnesses or Conditions: Participants who have the following co-morbidities are excluded:
- a. Confirmed diagnoses of the following sleep disorders: Narcolepsy, Restless Leg Syndrome, Circadian Rhythm Disorders
 - b. Confirmed diagnosis of Sleep Apnea that is untreated or not well controlled
 - c. Current or prior psychotic disorder
 - d. Current or prior Substance Abuse Disorder
 - e. Current or prior cardiac dysrhythmias (for example, atrial fibrillation, supraventricular tachycardia)
 - f. Currently pregnant, planning to become pregnant in the next 1 month, or breastfeeding
 - g. Allergies or adverse reactions (for example, anxiety) to Montmorency tart cherry extract and/or Venetron®

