3.3 Duration of Participation and Overview of What is Expected from Participants

Participants will complete a 5-week study consisting of screening assessments, baseline scales and surveys, objective digital measure, 2 weeks of product use (1 week on - 1 week off - 1 week on), scales and surveys, and end of study assessments and surveys. This is a remote observational study that will use the People Science app-based data collection platform Consumer Health Learning and Organizing Ecosystem (CHLOE) for study participants to report their assessments and collect objective sleep data from personal wearable devices. Participants will receive the study product during the baseline period. Demographic and medical history data will be collected for the study.

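### The off week starts the day after the last dose, with no carry-over check and no rule assigning nights to periods, so the on/off contrast could be diluted; the baseline versus end-of-study test in Section 9.6 is not affected

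*Combined protocol and SAP*

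**What the plan says.** - **Comparator.** Section 1.0 sets two references for the primary endpoint, baseline and the off week: "Change in average sleep quality score by 1 point as measured by daily 10-point visual analogue rating scale (VAS) from baseline and 1 week of" (the quote stops just before the off week is named). Alertness and the wearable endpoints use the same two references, for example "Change in average nightly sleep duration as measured via personal health tracking wearable device from baseline and 1 week of no product use". Section 9.3 also treats product use and no product use as two arms.
- **Sequence.** Everyone follows one order: "2 weeks of product use (1 week on - 1 week off - 1 week on") after a baseline week (Section 3.3).
- **Timing.** Section 6.1 has participants "Administer nightly dose of study product 30-60 minutes prior to lying down in bed through Day 14", followed at once by the "No Product Use Period (Day 15 to Day 21"). There is no gap and no night is excluded.
- **Washout standard.** Inclusion criterion 5 in Section 3.2 requires "Willingness to do a minimum of 1 week wash out of current OTC or other products for sleep (e.g. melatonin, anticholinergics"). Section 2.1 says of one ingredient: "Montmorency tart cherry is a special kind of cherry that is known to provide a natural source of melatonin".
- **Survey reference.** The daily survey asks about the previous night's sleep and alertness since waking (Table 4.1 footnote d; Section 6.1). No section says which period a given survey belongs to.
- **Analysis.** The primary comparison written in Section 9.6 is baseline against end of study. Mixed models are to follow. No carry-over term, exclusion of nights or early/late check is described.

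**The concern.** All participants take the periods in the same order, so the off week is the only reversal in the design. It is what could separate a product effect from a steady time trend. If some of the effect persists after Day 14, the off-week average is not a clean unexposed value, and the on/off difference is pulled toward zero. If the effect also builds up over several nights, the product-week average is low as well, and the contrast shrinks from both sides.

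A second problem needs no pharmacology. The Day 15 survey describes the night of Day 14, when product was taken. Unless nights are assigned deliberately, the off week includes a product night.

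At stake are the off-week contrasts named in Section 1.0 and any mixed model that uses on/off exposure. A weak contrast could be taken for lack of effect, and a check devised after the data are seen would look selective.

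**Working it through.** **1. The plan's own figure.** Section 9.1 gives SD 2, correlation 0.50, difference 1, two-sided alpha 0.05, a Wilcoxon signed-rank test and 47 evaluable participants.
- SD of the paired difference = sqrt(2 × 2² × (1 − 0.5)) = 2.
- A paired t-test needs n = 44 for 90% power. Allowing for Wilcoxon efficiency, 44 × π/3 = 46.1, rounded up to 47.
- Power at n = 47 is 0.906 (noncentral t with 47 × 3/π), or about 0.907 by simulation under normality.

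The stated 47 and 90% reproduce, for an undiluted 1-point difference.

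**2. Grouping by calendar day, no carry-over.** This takes the first dose as the night of Day 8.
- Surveys on Days 15 to 21 rate nights 14 to 20: 1 product night and 6 off nights.
- Surveys on Days 8 to 14 rate nights 7 to 13: 1 off night and 6 product nights.
- Expected contrast = 6/7 − 1/7 = 5/7 = 0.71 of the true effect.
- Power for a true 1-point on/off difference, with SD of the difference 2 and n = 47, falls from about 0.91 to about 0.65.

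**3. Carry-over, with nights assigned correctly.** The documents give no offset time, so a half-life h (in nights) is assumed, with onset at the same rate.
- Effect on product night k = 1 − 0.5^(k/h).
- Effect on off night k = (1 − 0.5^(7/h)) × 0.5^(k/h), so decay starts from the level reached on product night 7.

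Week 2 versus Week 3, as a percentage of the full effect:

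| h (nights) | On, 7 nights | Off, 7 nights | Contrast | On, last 4 | Off, last 4 | Contrast |
|---|---|---|---|---|---|---|
| 1 | 86 | 14 | **72** | 97 | 3 | **94** |
| 2 | 69 | 29 | **40** | 84 | 15 | **69** |
| 3 | 56 | 35 | **21** | 71 | 23 | **48** |

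At h = 3, Week 4 versus Week 3 recovers slightly more: 28% over 7 nights and 52% over the last 4.

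**4. Precision cost of using late nights.** Assume independent night-to-night variation with SD s from 1 to 2. With 7 nights per period the variance of the difference is 4, so SE = sqrt(4/47) = 0.292. With m nights per period the variance is 4 − 2s²/7 + 2s²/m.
- m = 4: variance 4.21 (s = 1) to 4.86 (s = 2); SE 0.299 to 0.321, which is 3% to 10% larger.
- m = 2: variance 4.71 to 6.86; SE 0.317 to 0.382, which is 9% to 31% larger.

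The second case can arise because Section 9.3 accepts 60% completion. If the off week is the whole no-product arm, 60% of 7 is 4.2, so 5 completed days suffice. Three of those may be early nights, which leaves 2 late ones.

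**The case against.** The strongest reply is that the only primary test written out in Section 9.6 compares baseline with end of study. It does not use the off week, so off-week carry-over cannot dilute it. That stands. A reader might infer that the powered primary result is weakened; the documents do not support that.

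The washout argument is also an analogy. Inclusion criterion 5 is a general eligibility minimum and says nothing about how long this product acts. The melatonin statement concerns the tart cherry ingredient, not the finished product. Section 6.1 itself places the start of that washout ("Begin discontinuation of non-prescription products used for sleep") in the baseline week and still uses that week as a reference. It is therefore tempting, but not supported, to say that carry-over does occur. Rebound on stopping would enlarge the contrast instead.

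Three further points are fair:
- If a full week really were needed, the last 4 nights would not be clean either. The cut at 4 reduces the problem and does not remove it.
- The off week is open-label and participants see their own data in real time (Section 12.4), so it does not control expectation.
- A flat Week 3 is not wholly unreadable. Without a time trend, persistence predicts Weeks 2 and 3 both above baseline, and no effect predicts neither.

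What remains is that Section 1.0 names the off week as a comparator, no section assigns nights to periods, and Section 9.6 has no check on either problem.

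**Conclusion.** The point holds as a conditional weakness of the off-week contrasts for sleep quality, alertness, sleep duration and sleep latency, and of any mixed model using on/off exposure. It does not reach the baseline versus end-of-study test.

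The size of any carry-over is unknown. The recovery figures in the table rest wholly on assumed half-lives with matching onset. Restricting to late nights recovers more of the effect in each case, without full recovery.

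The night-assignment problem rests on the documents' own timing. Its loss, to 5/7 of the effect, arises only if surveys are grouped by calendar day, which the plan neither requires nor rules out.

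**What to change.** In Section 9.6:
1. Reconcile the comparator with Section 1.0, stating which contrast is primary and what role the off week has.
2. Assign each survey and each wearable night to a period by whether product was taken on that night, not by the date of the survey.
3. Pre-specify, as a sensitivity analysis beside the 7-night result, the on/off contrast from the last 4 nights of each period for the four nightly outcomes, with night-within-period plots.
4. Report a larger late-night contrast, with its confidence interval, only as consistent with carry-over. Do not adopt a rule that reads a null 7-night result as carry-over whenever the late-night contrast is larger. With no true effect, the late-night contrast exceeds the 7-night one in about 50% of null results (simulated with n = 47, SD of the difference 2, night-to-night SD 1 or 2).

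**Cost.** SAP wording and one extra model per endpoint, on data already collected. The late-night estimate is less precise, by the amounts in step 4 of the working, and depends more on surveys completed late in each week. The dosing schedule is unchanged. The fix does not repair the ISI: it recalls two weeks (Section 2.2), so the Day 22 score covers the first product week as well as the off week.
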